Appendix F: Participating Investigators and Institutions

The complete list of participating investigators and institutions will be provided under separate cover upon request.

Appendix H: Previous Clinical Investigations

A complete bibliography and summary of relevant literature, summary and results of preclinical testing, and summary of results of previous clinical investigations is provided in the Investigator's Brochure.

EV ICD Pilot Study Clinical Investigation Plan

MDT17034

Version 1.0, 02-MAR-2018

Page 132 of 133

Medtronic

## 1. Version History

Version	Summary of Changes	Author(s)/Title
1.0	
 
Not Applicable, New Document
 
	[name], Sr. Principal Statistician
2.0	
 
Make document ISO 14155:2020 compliant. Updated from the previous ISO 14155:2011 compliant version 1.0
 
	[name], Sr. Statistician
2.1	
 
There were several comments in version 2.0 that were left in the document and had not yet been resolved. Those comments were addressed and removed. The changes made included               
 
Removed redundant and unnecessary methodological comments in Section 7.9
 
Removed extra spaces around hyphens throughout document
 
Added the SAP version date and am now using the 'C' template for the document
 
 
 
	[name], Sr. Principal Statistician

## 2. List of Abbreviations and Definitions of Terms

Abbreviation	Definition
ATP	Antitachycardia pacing
EV	Extravascular
ICD	Implantable cardioverter defibrillator

## 3. Introduction

Today, implantable cardioverter defibrillator (ICD) therapy is the treatment of choice for patients who are at risk for sudden cardiac death due to life-threatening ventricular arrhythmias. Traditional ICD systems with transvenous leads are considered standard of care for primary or secondary prevention of arrhythmic death. However, these systems have limitations. Short- and long-term complications arising from ICD systems with transvenous leads, such as infection, pneumothorax, venous thrombosis, lead dislodgement, lead malfunction, and lead perforation, have persisted for decades as impediments to ICD usage. As a result, there is demand for novel ICD systems that circumvent the potential disadvantages of transvenous ICD systems by preserving the heart and vasculature.

Medtronic has developed an extravascular ICD system which uses a substernal lead vs. a transvenous or a subcutaneous lead. The Extravascular (EV) ICD system will have the capability, similar to a transvenous

system, to deliver ATP, post-shock pacing, and backup asystole pacing from a single device, while avoiding leads in the heart or vasculature.

The purpose of the EV ICD Pilot study is to characterize the preliminary safety and efficacy of the EV ICD system: a complete extravascular ICD system with the lead implanted substernally. The use of a pilot study design allows characterization of the EV ICD system in a limited number of subjects before launching into a large-scale pivotal study.

This Statistical Analysis Plan has been designed to document, the EV ICD Pilot Study design and the planned analyses to be included in interim and final reports.

## 4. Study Objectives

---

Primary Safety Objective: Characterize the freedom from major complications related to the EV ICD system and/or procedure at 3-months post-implant

Primary Efficacy Objective: Characterize the EV ICD defibrillation testing success rate at implant

Ancillary Objectives:

- Characterize appropriate and inappropriate shocks
- Characterize electrical performance (pacing capture thresholds, pacing impedance, sensing amplitudes) in a variety of postures and respiration cycles over time
- Characterize pacing sensation
- Characterize asystole pacing
- Characterize lead position over time
- Summarize Antitachycardia Pacing (ATP) performance with spontaneous arrhythmias
- Summarize adverse events

## 5. Investigation Plan

---

The EV ICD Pilot Study is a prospective, multi-center, single-arm, nonrandomized study. Up to 35 subjects will be enrolled at up to 10 sites in Australia and New Zealand. Subjects with a class I or IIa indication for single-chamber ICD therapy will be recruited and implanted with the Medtronic EV ICD system, which features defibrillation capability, as well as ATP and bradycardic pacing capability. Patients with a bradycardia pacing or cardiac resynchronization therapy indication are excluded. Subjects will undergo defibrillation testing at implant, as well as pacing threshold assessments at Pre-Hospital Discharge, 2 Weeks, 4-6 Weeks and 3 Month Visits. Subjects will subsequently be followed up at 6-Months post-implant and every 6 months thereafter until study closure. For further details regarding the investigational plan, see the EV ICD Pilot Clinical Investigation Plan.

## 6. Determination of Sample Size

---

At least 20 and up to 35 subjects will be implanted with the investigational EV ICD system. This is to gather early data with regard to patient safety and device efficacy. The sample size is not pre-specified to satisfy hypothesis testing statistical requirements, but rather to allow for multiple investigational sites enrolling patients and implanting the EV ICD system.

## 7. Statistical Methods

---

### 7.1 Study Subjects

#### 7.1.1 Disposition of Subjects

This is a single-arm study. Subjects who are consented will undergo implant of the EV ICD system, with required defibrillation, sensing, and pacing testing. At enrollment, subjects consent to have the EV ICD system implanted. Subjects will then return for 2 week, 4-6 weeks, 3 and 6 month visits, as well as every 6 months thereafter. A STROBE diagram will show each of these stages of follow-up through 30 months or beyond if needed, with categories for missed visit, death and exit. Screening log is not used in this study given the poor compliance to the use of it in the past.

#### 7.1.2 Clinical Investigation Plan (CIP) Deviations

Study deviations will result in corresponding Study Deviation eCRFs being completed. These deviations will be summarized with descriptive statistics including, for each type of deviation, how many occurrences there were in the study, and the number of subjects experiencing each type of deviation. Inclusion/exclusion violations will not result in subjects being excluded from analysis of objectives. Of particular importance will be required testing not completed at implant or follow-up.

#### 7.1.3 Analysis Sets

All enrolled subjects who undergo an EV ICD implant attempt will be included in the evaluation of the safety objective, and all subjects who undergo implant defibrillation testing will be included in the evaluation of the primary efficacy objective. Descriptive statistics will be used to summarize results.

### 7.2 General Methodology

Data analysis will be performed by a Medtronic statistician or designee.

All analyses will be performed on an “As Treated” basis. The cohort will include all enrolled subjects who undergo the study procedures, and there are no prespecified subgroups for assessment. For endpoints involving only measurements collected at follow-up visits, only subjects who complete those visits will be included in the analysis of those endpoints.

### 7.3 Center Pooling

Due to the feasibility nature of this study and reduced sample size, statistical comparisons of sites' performance will not be performed.

### 7.4 Handling of Missing, Unused, and Spurious Data and Dropouts

All available data will be included in the data listings and tabulations. Imputation of values for missing data for primary and secondary efficacy analyses will not be performed. With regard to the safety primary objective, subjects who exit the study prior to experiencing a major system or procedure-related complication will be censored at the date of their exit (in the case of the subject being lost to

follow-up, the subject will be censored at the date of last contact with the subject) in the calculation of any Kaplan-Meier freedom from complication rates.

## 7.5 Adjustments for Multiple Comparisons

No adjustments will be made for multiple comparisons, as descriptive statistics will primarily be used.

## 7.6 Demographic and Other Baseline Characteristics

Descriptive statistics will be used to summarize all implant procedure information collected, including

- Lead insertion
- Sensing testing
- Closure
- Operative Time: Time of First Incision to Time at final suture/procedure stop

## 7.7 Treatment Characteristics

Descriptive statistics will be used to summarize all implant procedure information collected, including

- Lead insertion
- Sensing testing
- Closure
- Operative Time: Time of First Incision to Time at final suture/procedure stop

## 7.8 Interim Analyses

Once all enrolled subjects have had the opportunity to undergo implant defibrillation testing, the data at implant will be assessed for submission to one or more regulatory agencies. It will accompany data acquired through the point at which all subjects have had the opportunity to be followed to a 3-month visit, the accumulated data will be summarized for possible external dissemination. Descriptive statistics will be used to summarize the data.

## 7.9 Evaluation of Objectives

### 7.9.1 Primary Objective #1

Characterize the freedom from major complications related to the EV ICD system and/or procedure at 3 months post-implant.

#### 7.9.1.1 Hypothesis

This trial is for the purposes of gathering preliminary data on the investigational product, and so there are no hypotheses for this objective.

#### 7.9.1.2 Performance Requirements

Performance requirements are not pre-specified for this objective. The endpoint is defined as a subject's first occurrence of a major complication related to the EV ICD system and/or procedure as determined

by the independent Clinical Event Committee (CEC) that occurs on or prior to 3-months (90-days) post-implant.

For an adverse event to meet the endpoint, the event must have occurred within 90 days (inclusive) of the EV ICD system implant and be adjudicated by the CEC as being a major complication related to the EV ICD system and/or procedure. Major complications are those complications resulting in:

- Death
- Permanent loss of defibrillation function due to mechanical or electrical dysfunction of the device
- Hospitalization
- Prolonged Hospitalization by at least 48 hours
- System revision (reposition, replacement, explant)

### 7.9.1.3 Rationale for Performance Criteria

This is an observational study, and this objective is for the purpose of gathering data pertaining to device safety over the first 3 months post-implant. There are no pre-specified performance criteria.

### 7.9.1.4 Analysis Methods

Results will be summarized in aggregate using descriptive statistics. The 90-day freedom from major complication rate will be generated using the Kaplan-Meier method, and the total number of major complications experienced by subjects for whom an implant is attempted will be summarized.

### 7.9.1.5 Determination of Patients/Data for Analysis

All subjects for whom an implant of the investigational product is attempted will be included in the analysis.

## 7.9.2 Primary Objective #2

Characterize the EV ICD defibrillation testing success rate at implant.

### 7.9.2.1 Hypothesis

This trial is for the purposes of gathering preliminary data on the investigational product, and so there are no hypotheses for this objective.

### 7.9.2.2 Performance Requirements

Performance requirements are not pre-specified for this objective. The endpoint, defibrillation testing success, is defined as:

- Single SSVA conversion at 20J, or
- Conversion of two successive episodes of SSVA at 30J in final system configuration.

Notes:

- In one of the two successive SSVA episodes, up to two 30J shocks are permitted

- To achieve final system configuration, changing the position of the ICD generator and/or the lead or changing shock polarity is permitted
- Subjects can return for testing on another day if testing is not fully completed on the day of implant.

### 7.9.2.3 Rationale for Performance Criteria

This is an observational study, and this objective is for the purpose of gathering data pertaining to defibrillation efficacy at implant. There are no pre-specified performance criteria.

### 7.9.2.4 Analysis Methods

Results will be summarized in aggregate using descriptive statistics. Subjects will be partitioned by the results of their defibrillation testing (e.g., no rescue shocks required, one rescue shock required), with counts and percentage falling into each subgroup reported.

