In order to develop and evaluate a newly designed system for the substernal space, Medtronic completed pre-clinical research evaluations of substernal defibrillation, pacing, and sensing, and subsequently initiated three human clinical research feasibility studies with 119 enrollments to explore the potential development of a future chronic implantable extravascular defibrillation system with a lead implanted in the substernal space. Both pre-clinical and clinical data are described in further detail within the Investigator’s Brochure.

The first human clinical feasibility study, Acute Substernal Defibrillation (ASD) showed substernal defibrillation is feasible with energy available in current transvenous ICDs, with defibrillation successful in 13 of 14 subjects (93%) at 35J (95% CI: 74.7% - 99.8%). VF duration was 18.4 ± 5.6 sec. One failure was associated with high and lateral shock coil placement²¹. The second human clinical feasibility study, Substernal Pacing Acute Clinical Evaluation (SPACE) in which 26 subjects underwent pacing evaluation, showed that pacing should be possible in nearly all patients from the extravascular substernal location²². The third human clinical feasibility study, Acute Extravascular Defibrillation, Pacing and Electrogram (ASD2), was designed to further assess study pacing thresholds and defibrillation efficacy via substernal therapy delivery in a larger cohort as well as collect additional data, mainly multi-vector substernal electrograms during induced VF/VT and intrinsic rhythms directly from an investigational lead placed in the substernal space. There were 79 subjects who underwent the ASD2 procedure, and 125 VF/PVT episodes were successfully collected from 68 subjects for algorithm development and validation of the current EV ICD system used in this EV ICD Pilot Study. In addition, this study highlighted the importance of training and procedure support for the chronic device implant, which is further outlined within this CIP. At the time of this report, the final report has been completed and an abstract has been submitted.

In summary, human acute feasibility data from 119 patients have contributed to the advancement of the Extravascular ICD program, and the refinement of the device and algorithm, and the implant procedure, and provide assurance for the initiation of this study with first-in-human chronic device implant of the EV ICD system.

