8.6.7. VF induction and Defibrillation Testing

8.6.7.1. General Requirements

In order to ensure subject safety in an ambulatory setting, VF induction and defibrillation testing is required at implant. Adjust device programming to ensure adequate safety margins for sensing and defibrillation during VF induction testing.

Ensure a Wavelet template is collected prior to induction. Induction of VT/VF will be achieved using one of the following methods:

- a. Burst Induction (Coil2-Coil1, 40V).
- b. T-shock (up to 20J).

Follow the defibrillation testing as outlined in Figure 8.2, beginning at Episode 1 (20J). The testing protocol may require up to five (5) sustained shockable ventricular arrhythmia (SSVA) episodes induced and up to seven (7) EV ICD shocks delivered (Figure 8.2).

Ensure EV ICD VF detection is enabled prior to performing induction. If the subject's health is at risk, defibrillation testing should be suspended or terminated.

Defibrillation testing success is defined as:

- a. Single SSVA conversion at 20J, or
- b. Conversion of two successive episodes of SSVA at 30J in final system configuration.

Notes:

- In one of the two successive SSVA episodes, up to two 30J shocks are permitted
- To achieve final system configuration, changing the position of the can and/or the lead or changing shock polarity is permitted
- Subjects can return for testing on another day if testing is not fully completed on day of implant.

Ensure an external transthoracic defibrillation system is present and ready to deliver rescue shocks during defibrillation testing.

The NID for EV ICD initial detection should be programmed as 30/40 for the first induction in order to capture sufficient length of recorded SSVA. Subsequent inductions will be performed using NID for initial detection = 18/24.

The NID for Redetection (where applicable) should be programmed as NID 9/12.

It is recommended to wait 5 minutes between the end of an SSVA episode and subsequent induction. Waiting period after failed induction attempts is at the investigator's discretion.

Reminder: Print live strip for the duration of each SSVA episode. Ensure a copy of the live strip is sent to Medtronic (e.g. a scan). Print the VT/VF episode report and store at the site.

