8.6.7.9. Unsuccessful Implant Definition

Implant procedure/testing is considered unsuccessful if any of the following occur:

- EV ICD System is not fully implanted
- Defibrillation testing does not meet criteria for success
- R-wave < 1mV for all possible sensing vectors after troubleshooting methods are exhausted

If the subject completes the initial implant procedure without completing the defibrillation testing, the subject may be brought back prior to pre-hospital discharge to complete the defibrillation testing, as outlined in Figure 8.2.

If the EV ICD system is explanted or repositioned after initial implant procedure but prior to pre-hospital discharge, this should be captured on a system modification eCRF. In the event of the EV ICD being permanently explanted, these subjects should be followed and assessed for AEs through 30 days or until procedure or system related AEs have been resolved, at which point subjects can be exited.

An unsuccessful implant procedure, and unsuccessful or incomplete testing (including prolongation of hospital stay by allowing time to minimize transient factors affecting defibrillation) are not considered adverse events; however, any adverse events occurring during an unsuccessful implant attempt (e.g., subject allergy to electrodes used during implant) must be recorded and classified. Subjects with an unsuccessful EV ICD attempt will be followed up through 30 days or until procedure or system related AEs have been resolved, at which point they can be exited.

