12.1. General Considerations

Data analysis will be performed by a Medtronic statistician or designee.

All analyses will be performed on an "As Treated" basis.

The cohort will include all enrolled subjects who undergo the study procedures, and there are no pre-specified subgroups for assessment. For endpoints involving only measurements collected at follow-up visits, only subjects who complete those visits will be included in the analysis of those endpoints.

Any tests of treatment effects will be conducted at a two-sided alpha level of 0.05 unless otherwise stated.

A Statistical Analysis Plan (SAP) will be developed and kept under separate cover and will include a comprehensive description of the statistical methods and reports to be included in the final study report, as well as a description of how missing, unused, and spurious data will be accounted for. Any change to the data analysis methods described in the protocol will require an amendment only if it changes a principal feature of the protocol. Any other change to the data analysis methods described in the protocol, and the justification for making the change, will be described in the clinical study report.

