### 7.9.2.5 Determination of Patients/Data for Analysis

All subjects for whom defibrillation testing is attempted with the investigational device will be included in the analysis.

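### Does the SAP need a stated outcome for a subject in whom defibrillation testing is attempted but no arrhythmia is ever induced?

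*SAP*

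**What the plan says.** Success has two routes in SAP 7.9.2.2 (repeated in protocol 12.4.2). The first is "Single SSVA conversion at 20J"; the second is conversion of two successive episodes at 30J. Both presuppose an induced SSVA.

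For the display of results, SAP 7.9.2.4 says "Subjects will be partitioned by the results of their defibrillation testing (e.g., no rescue shocks required, one rescue shock required"), with a count and a percentage for each group.

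The denominator is described twice. SAP 7.9.2.5 says "All subjects for whom defibrillation testing is attempted with the investigational device will be included in the analysis". SAP 7.1.3 says "all subjects who undergo implant defibrillation testing will be included in the evaluation of the primary efficacy objective". Neither verb is defined.

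The protocol foresees that induction may not work. Section 8.6.7.1 mentions a "Waiting period after failed induction attempts" and leaves its length to the investigator. Section 8.6.7.9 begins a sentence "An unsuccessful implant procedure, and unsuccessful or incomplete testing", which treats incomplete testing as distinct from unsuccessful testing. It also allows a subject to be brought back before discharge to finish testing.

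Protocol 12.1 says the SAP will contain its statistical methods "as well as a description of how missing, unused, and spurious data will be accounted for". SAP 7.4 answers that all available data go into listings and tabulations and that efficacy values are not imputed. SAP 7.1.2 summarises deviations and singles out required testing that was not completed.

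**The concern.** A subject in whom testing is attempted and no SSVA appears, even on a return visit, meets neither success route. Read literally, that subject stays in the denominator and looks the same as a subject whose shocks failed, although the system delivered no therapy shock. An analyst who leans on the wording of 7.1.3, or who treats the result as missing under 7.4, could drop the subject instead. Two readings then give two primary rates.

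The breakdown in 7.9.2.4 could add to the confusion. Its only named groups are counts of rescue shocks, and a subject who was never induced needed none. Used alone, those groups would place the subject with the best performers. The rate is one of two primary results, and SAP 7.8 says the implant data will be assessed for regulatory submission.

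**Working it through.** The plan states no expected success rate or power for this endpoint, so there is no figure to reproduce.

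**1. Following the subject through the text.**
- SAP 7.9.2.5: testing was attempted, so the subject is included.
- SAP 7.9.2.2: no SSVA was converted, so the subject is not a success.
- Protocol 8.6.7.9: testing that does not meet the success criteria makes the implant or testing unsuccessful, which agrees with that classification.
- SAP 7.9.2.4: the breakdown is by test result, and the rescue-shock groups are introduced by e.g., so a not-induced group is permitted but not named.

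**2. Effect on the rate.** Let N be subjects attempted, k not induced and s successes. The all-attempted rate is s/N and the rate among induced subjects is s/(N − k). The difference is s·k/[N(N − k)], which reduces to k/N when there are no shock failures. For one subject that is 1/20 = 5.0 points or 1/35 = 2.9 points. The planned 20 to 35 implants stand in for the number tested, and k is assumed. Intervals are exact (Clopper-Pearson) 95%.

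| N | Shock failures | k | s/N | s/(N − k) |
|---|---|---|---|---|
| 20 | 0 | 1 | 19/20 = 95.0% (75.1–99.9) | 19/19 = 100% (82.4–100) |
| 20 | 0 | 3 | 17/20 = 85.0% (62.1–96.8) | 17/17 = 100% (80.5–100) |
| 35 | 0 | 1 | 34/35 = 97.1% (85.1–99.9) | 34/34 = 100% (89.7–100) |
| 35 | 0 | 5 | 30/35 = 85.7% (69.7–95.2) | 30/30 = 100% (88.4–100) |
| 35 | 2 | 3 | 30/35 = 85.7% (69.7–95.2) | 30/32 = 93.8% (79.2–99.2) |

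In the last row the difference is 30 × 3/(35 × 32) = 8.0 points, about 2.7 per subject. The literal reading always gives the lower figure.

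**3. The rescue-shock groups.** Protocol 8.6.7.2 calls for an external rescue after a failed 20J shock, so every 30J-route passer and every shock failure has at least one. Section 8.6.7.3 also calls for one when the 15J shock fails in a subject who has already passed at 20J. If that rescue is counted, the zero-rescue group holds only 20J passers who converted at 15J plus any subjects never induced. With N = 35, k = 5 and the other 30 converting at both energies, success is 30/35 = 85.7% while zero rescue is 35/35 = 100%. The two figures conflict only if the examples are used as the complete set of categories.

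**4. How often.** The documents do not say. Protocol 3.1 reports of the earlier acute study: "There were 79 subjects who underwent the ASD2 procedure, and 125 VF/PVT episodes were successfully collected from 68 subjects". That leaves 79 − 68 = 11 without a collected episode, 11/79 = 13.9% (7.2–23.5), which would correspond to 2.8 of 20 or 4.9 of 35. The reason is not given, and the passage does not say induction was tried in all 79, so this is neither an induction-failure rate nor an upper bound on one. At assumed rates of 2%, 5% and 10%, the chance of at least one case, 1 − (1 − r)^N, is 33%, 64% and 88% among 20, and 51%, 83% and 97% among 35. Two induction methods and the return visit should reduce the number left without an SSVA at the end.

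**The case for a change.** The best case for amending runs as follows. In a purely descriptive study the categories are the analysis. Fixing them after the results are known, in a single-arm study analysed by the sponsor's statistician, is what an SAP should prevent. Protocol 12.1 passed the question to the SAP, and the SAP did not take it up. Even at an assumed 2%, one such subject among 35 is about an even chance. The remedy would be a sentence and a table row.

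Part of this stands. The text names no outcome for this subject, the two denominator statements use different verbs, and dropping the subject is conceivable.

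The harm does not follow, though. Dropping the subject goes against 7.9.2.5, the more specific provision. The argument that a reader could not separate failed shocks from failed inductions overlooks the listings in SAP 7.4, the deviation summary in 7.1.2 and the recording of each shock outcome under protocol 8.6.7.1. With at most 35 subjects, those sources should identify each one who was never shocked. Whether the case report forms record failed induction attempts cannot be checked, because the forms are under separate cover. Figure 8.2, the testing flow diagram, was not visible in the copy reviewed and may contain a branch for this case.

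**Conclusion.** No change is needed. This is missing detail that competent analysts would fill sensibly, and following the text literally does not give a flattering or invalid result. The all-attempted rate is conservative: each never-induced subject costs 5.0 points at 20 and 2.9 points at 35 when no shocks fail, and slightly less when some do. SAP 7.9.2.1 to 7.9.2.3 attach no hypothesis, performance requirement or criterion to the rate, so no decision changes with the classification. A breakdown by test result already accommodates a not-induced row. Showing a second rate among induced subjects, or tabulating by testing episode, is a reporting preference.

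This rests on three assumptions: that the number tested is close to the 20 to 35 planned implants, that few subjects remain without an SSVA after retesting, and that analysts treat the rescue-shock groups as the examples they are. The frequency of failed induction is unknown from the documents.

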Record shock outcome and shock impedance (if available) for each EV ICD and rescue shock. A shock will be considered successful if it results in termination of the induced SSVA episode, with termination defined as a return to normal intrinsic rhythm or to a supraventricular tachycardia before the next shock is given.

[figure not shown]

Figure 8.2: Diagram outlining the process of SIVA induction and defibrillation testing.

8.6.7.2. Episode 1

Program Rx1 and Rx2 therapies as follows:

	Rx1	Rx2- Rx6
NID	30/40	NA
Redetect NID	NA	NA
VF Therapy Status	ON	OFF
Energy	20J	NA
Pathway	STD	NA

EV ICD Pilot Study Clinical Investigation Plan

MDT17034

Version 1.0, 02-MAR-2018

Page 52 of 133

[figure not shown]

If Episode 1, Rx1 is successful in terminating the episode, the EV ICD System will have passed Implant Criteria. Proceed with Section 8.6.7.3, Episode 2 testing at 15J for better characterization of defibrillation threshold in the subject.

If Episode 1 shock was not successful, an external defibrillator should be used to deliver the rescue shock. Proceed to Section 8.6.7.3, Episode 2.

8.6.7.3. Episode 2

If Episode 1 was Successful, test at 15 J			If Episode 1 was Unsuccessful, test at 30J			
	Rx1	Rx2 – Rx6		Rx1	Rx2	Rx3 – Rx6
NID	18/24	NA	NID	18/24	NA	NA
Redetect NID	NA	NA	Redetect NID	NA	9/12	NA
VF Therapy Status	ON	OFF	VF Therapy Status	ON	ON	OFF
Energy	15J	NA	Energy	30J	30J	NA
Pathway	STD	NA	Pathway	STD	REV	NA

Record whether 15J was successful in terminating SSVA Episode.
 
If shock fails to terminate the SSVA episode, an external defibrillator should be used to deliver the rescue shock. The EV ICD System is still considered to have met Implant Criteria via a single 20J shock in Episode 1.
			
If Rx1 or Rx2 is successful in Episode 2, continue to Episode 3.
 
If both Rx1 and Rx2 fail in Episode 2, consider taking one or more recommended steps at improving the chance of shock success as outlined in Section 8.6.7.5 and continue to Episode 4.
			

8.6.7.4. Episode 3

If Episode 2, Rx1 was successful				If Episode 2, Rx2 was successful			
	Rx1	Rx2	Rx3-Rx6		Rx1	Rx2	Rx3-Rx6
NID	18/24	NA	NA	NID	18/24	NA	NA
Redetect NID	NA	9/12	NA	Redetect NID	NA	NA	NA
VF Therapy Status	ON	ON	OFF	VF Therapy Status	ON	OFF	OFF
Energy	30J	30J	NA	Energy	30J	NA	NA
Pathway	STD	STD	NA	Pathway	REV	NA	NA

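### Does the primary efficacy breakdown in SAP 7.9.2.4 need a rule on whether an external rescue after the 15J episode counts?

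*SAP*

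**What the plan says.** SAP 7.9.2.4 and Protocol 12.4.4 use the same sentence for the analysis of defibrillation success: "Subjects will be partitioned by the results of their defibrillation testing (e.g., no rescue shocks required, one rescue shock required"), reporting the number and percentage in each group. Neither document defines a rescue shock for this table.

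The endpoint itself is fixed in SAP 7.9.2.2. A subject succeeds with one conversion at 20J, or by the second route: "Conversion of two successive episodes of SSVA at 30J in final system configuration". The denominator in SAP 7.9.2.5 is everyone in whom testing is attempted.

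The testing sequence is in Protocol 8.6.7. The general requirements use the term for the external shock: "Ensure an external transthoracic defibrillation system is present and ready to deliver rescue shocks during defibrillation testing". Two external rescues are then written out.

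- Episode 1, 20J (8.6.7.2): "If Episode 1 shock was not successful, an external defibrillator should be used to deliver the rescue shock".
- Episode 2, 15J, given only after a 20J pass (8.6.7.3): "If shock fails to terminate the SSVA episode, an external defibrillator should be used to deliver the rescue shock".

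On the status of the subject, the protocol says of the 20J shock: "If Episode 1, Rx1 is successful in terminating the episode, the EV ICD System will have passed Implant Criteria". Of a later 15J failure it says: "The EV ICD System is still considered to have met Implant Criteria via a single 20J shock in Episode 1".

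**The concern.** A rescue count looks like a measure of how hard it was to reach success, but the 15J episode breaks that link. A subject who passed at 20J and then failed at 15J has had one external rescue. So has a subject who failed at 20J and then passed both 30J episodes without troubleshooting. If all external rescues count, these two share a row although they met the endpoint by different routes, and the no-rescue row becomes narrower than the group that passed at 20J.

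The implant data are to be assessed for regulatory submission (SAP 7.8), and the pilot is meant to describe the system before a pivotal study. A reader who took the no-rescue percentage as the 20J pass rate would be misled if the table had been built with 15J rescues included.

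**Working it through.** **Inputs.** The episode sequence in Protocol 8.6.7.2 to 8.6.7.7, the success definition in SAP 7.9.2.2 and the denominator in SAP 7.9.2.5. One assumption is added: one effective external shock whenever all programmed device therapies in an episode fail. The text states an external rescue only for the 20J and 15J failures. For failed 30J episodes it is inferred from Rx3 to Rx6 being off.

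**Check against the plan's own figure.** The longest route is a failed Episode 1 (1 shock), Episodes 2 and 3 with 3 shocks between them, and Episodes 4 and 5 with 3 shocks between them. That gives 1 + 3 + 3 = 7 device shocks in 5 episodes, which matches the maximum stated in Protocol 8.6.7.1. Enumerating every completed sequence gives 23 paths: 2 that pass at 20J, 3 that pass at 30J before troubleshooting, 9 that pass at 30J after troubleshooting, and 9 that fail (2 + 3 + 9 + 9 = 23).

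**Rescue count by route, completed tests.**

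| Route | All external rescues counted | Only rescues before the endpoint is met |
|---|---|---|
| 20J pass, 15J converts | 0 | 0 |
| 20J pass, 15J fails | 1 | 0 |
| 20J fail, 30J pass before troubleshooting | 1 | 1 |
| 20J fail, 30J pass after troubleshooting | 2 | 2 |
| Fails implant criteria | 3 | 3 |

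In the first column the one-rescue row holds 1 path that passed at 20J and 3 that failed at 20J. In the second column each count belongs to one outcome.

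**Incomplete tests.** Testing may be suspended or terminated (Protocol 8.6.7.1) or left incomplete (8.6.7.9), and such subjects stay in the denominator. A subject stopped after a failed 20J shock has one rescue and shares a count with the 30J passes. A subject stopped before any shock has none and shares a count with the 20J passes. So even the second column is one-to-one only for completed tests, and a sentence leaving out 15J rescues would not by itself give a clean table.

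**Effect on the endpoint.** A subject who passes at 20J and fails at 15J is a success under either count. Neither the numerator nor the denominator of the success rate uses the rescue count, so the change in that rate is 0.

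**Possible mixing, for scale only.** The documents give no rates for this system. Assume 35 subjects tested, 80% passing at 20J, and 10% to 50% of those failing at 15J.

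- 20J passes: 35 × 0.80 = 28.0.
- Moved to the one-rescue row if 15J rescues count: 28.0 × 0.10 = 2.8, up to 28.0 × 0.50 = 14.0.
- Left in the no-rescue row: 28.0 − 2.8 = 25.2 (72%), down to 28.0 − 14.0 = 14.0 (40%), against 28.0 (80%) if they do not count.

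These figures show that the two tables could look different. They are not estimates for this trial.

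**The case for a change.** The best argument for acting is that, apart from a general reference to descriptive statistics, this grouping is the only analysis specified for the primary efficacy objective. Protocol 12.1 promises a comprehensive description in the SAP, yet the SAP repeats the protocol sentence unchanged. Counting every rescue is also a natural literal reading: the 15J episode belongs to defibrillation testing, and Protocol 8.6.7.1 has the outcome of each rescue shock recorded with no exception for 15J. The overlap follows from the sequence and does not depend on the inference about failed 30J episodes.

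What stands is that the term is undefined and that one reading mixes routes. Three things keep this from being a defect.

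- The rule is to group by test result; the rescue labels only illustrate it. A table by 20J pass, 30J pass before or after troubleshooting, failure and incomplete test is already within the plan.
- The context favours leaving 15J out. The SAP never mentions 15J, its endpoint has only 20J and 30J routes, and the protocol runs the 15J episode after implant criteria are met, to describe the threshold further. Neither document says this outright.
- Nothing is lost in the data. The protocol instructs "Record whether 15J was successful in terminating SSVA Episode", outcomes are recorded for each device and rescue shock, and SAP 7.4 puts all available data in the listings. The 20J pass rate is not a planned estimate, but it can be recovered.

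**Conclusion.** No change to the plan is called for. This is a gap in the labelling of a descriptive table that an analyst can fill sensibly when laying out the output. The overall success rate and its denominator do not move, there is no hypothesis or performance criterion for the grouping to affect, and the data that distinguish the routes are collected. The size of any mixing cannot be derived from the documents; the ranges shown rest on assumed rates. The mapping of rescue counts to routes assumes one effective external shock per failed episode and holds only for completed tests. Presenting the result by endpoint route, with incomplete tests and the 15J result on separate lines, is a choice the present wording already allows.
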